8.4.2 SERIOUS ADVERSE EVENT REPORTING

8.4.2.1 Timeframes for Reporting SAEs

Under 21 CFR 312.32(c), the Sponsor is required to notify FDA and all participating investigators in a safety report of potentially serious risks from clinical trials [i.e., Suspected Unexpected Serious Adverse Reactions (SUSARS)], as soon as possible after the Sponsor receives the safety information and determines that the information qualifies for reporting:

- No later than 7 calendar days for events that are life threatening (in the opinion of the investigator or the Sponsor) or that involve Death as an outcome.
- No later than 15 calendar days for all other SUSARS.

As such, prompt notification of the Sponsor, and/or the Sponsor's representatives, and promptly providing requested follow-up information regarding SAEs is essential so that ethical and regulatory responsibilities and legal obligations can be satisfied. Investigators are responsible for reporting SAEs according to the following timeframes:

- All SAEs occurring during the study should be reported immediately.
- The SAE Report Form and relevant source documents, if applicable, must be completed and emailed to [contact] within 24 hours of observation or learning of the event.
- Follow-up information must be sent to the CRO within 24 hours of receipt of information by the investigational site.

SAEs will be followed until resolution, the condition stabilizes, the event is otherwise explained or is judged

by the investigator to be no longer clinically significant, or until the subject is lost to follow up.

8.4.2.2 SAE Information to Report

All information available regarding an SAE must be submitted in the timeframes indicated. At a minimum, SAE reports must contain the subject ID, the SAE verbatim term, onset date, relationship to study drug/causality, and a brief narrative of the event. Please note that **relationship to study drug/causality as well as the reported verbatim term are very important** and should be included in the initial report as it may impact expedited regulatory reporting requirements for the event. The date of SAE discovery by the site staff should be documented in the source documents.

The investigator must record all relevant information regarding an AE/SAE in the applicable sections of the CRF. It is not acceptable for the investigator to send photocopies of the subject's medical records in lieu of completion of the appropriate AE/SAE pages. However, there may be instances when copies of medical records for certain cases are requested by the CRO and/or the Sponsor. If medical records are submitted to the CRO then all subject personal identifiers must be completely and thoroughly redacted prior to submission.

A blank SAE Report Form and instructions for SAE reporting will be provided to the site and will be maintained in the investigator's study file. The SAE Report Form must be completed and emailed to [contact] according to the timeframes specified in [Section 8.4.2.1](#). The SAE Report Form should include copies of relevant source documents, if applicable. Reconciliation of any discrepancy noted during monitoring and amending the eCRF is required.

If new information about an SAE is received or corrections to data are needed, the investigator should complete a new SAE Report Form and check the "follow-up" box on the form. This follow-up SAE Report Form should be submitted within 24 hours of learning of the information, especially if the new information concerns seriousness, relatedness, or the event term of an AE.

The site, acting under their local IRB, should submit all applicable events, unanticipated problems, and safety reports to the site's local IRB, if applicable. All safety reporting deviations should also be submitted to their local IRB, if applicable.

8.4.3 ADVERSE EVENTS OF SPECIAL INTEREST

The following will be considered AEs of special interest (AESI):

- Clinically-significant peripheral edema or pulmonary edema.
- Reduced kidney function (eGFR < 45 mL/min/1.73 m²).
- Suspected transmission of blood-borne infectious agents.

AESI occurring during the study should be reported within 48 hours of observation or learning of the event, unless the event is serious, in which case the event must be reported according to the timeframes specified in [Section 8.4.2.1](#).

8.4.4 REPORTING OF PREGNANCY

While pregnancy itself is not considered an AE, pregnancy occurring in a clinical study must be followed to collect information regarding the experiences of gestation and pregnancy with study agent exposure. The investigator must report any pregnancy that occurs in a female study subject subsequent to first exposure to

the study agent until End of Study, or 3 months following a subject's last dose in the event of early termination. All pregnancies will be reported to the IRB, Sponsor, and CRO. In the event of a pregnancy, the subject will undergo continued safety follow-up through pregnancy outcome.

Any pregnancy must be followed by the investigator until delivery or to the end of pregnancy. Any anomalies, complications, abnormal outcomes, or birth defect(s) observed in the child must be reported as an SAE within 24 hours of the investigator or study personnel's first knowledge.

8.5 STUDY HALTING RULES

If any of the following safety events occur, a Safety Evaluation Meeting (defined below) will be triggered:

- Three or more SAEs in the same system/organ/class (SOC) that are assessed as possibly or definitely related to the study agent by the investigator and confirmed as such by the Sponsor (see [Section 8.2.2 Relationship to Study Agent](#)).
- Within or between any of the dosing groups: an overall pattern of symptomatic, clinical, or laboratory events associated with the study agent that the Sponsor's Program Physician or designee consider a serious potential safety concern (e.g., suspicious overall pattern).

Events that are more likely related to the infusion procedure, such as infiltration or hematoma, will not be considered "drug related" and will not contribute to the count of definitely-related SAEs that would trigger a Safety Evaluation Meeting.

Safety Evaluation Meeting

If safety events of potential concern occur during the trial (i.e., 3 related events in the same SOC or a suspicious overall pattern, as defined above) a Safety Evaluation Meeting may be triggered, and dosing may be temporarily halted based on the observations. The Sponsor will inform the FDA in the event of any temporary halt in dosing at any time during the conduct of the study. The purpose of the meeting is for the investigator, the Sponsor, and the CRO to discuss and evaluate the safety of the subjects using available aggregated safety data and without compromising study blinding, unless the Sponsor deems unblinding necessary for safety evaluation.

Attendants at the Safety Evaluation Meeting will include the Program Physician of Alkahest (or his/her designee), the CRO, and available active investigators participating in the trial. After sufficient data review the Sponsor will choose one of the following courses of action:

1. Continue dosing with no change to protocol.
2. Halt dosing in all groups and stop the study.
3. Continue with a modified protocol design and amend the protocol as appropriate.

8.6 SAFETY OVERSIGHT

Safety oversight will be provided by the Sponsor's Program Physician or his or her designee in concert with the site investigators. There will be no formal Data Safety Monitoring Board (DSMB) established. As needed, Safety Evaluation Meetings will be convened as described in [Section 8.5](#) to monitor the ongoing safety of the study. The Sponsor's Program Physician or designee is the final authority for safety oversight in the study.

9 CLINICAL MONITORING

Clinical site monitoring is conducted to ensure that the rights and well-being of human subjects are protected, that the reported trial data are accurate, complete, and verifiable, and that the conduct of the trial is in compliance with the currently approved protocol/amendment(s), with GCP, and with applicable regulatory requirement(s).

- Monitoring for this study will be performed by the study CRO in accordance with the Clinical Monitoring Plan (CMP).
- A mix of on-site and centralized monitoring will be performed to ensure the safety of clinical subjects and the accuracy and completeness of study data.
- The Sponsor will be provided with copies of monitoring reports per the timelines specified within the CMP.
- Details of clinical site monitoring tasks and scope are documented in the study's CMP. The CMP describes in detail who will conduct monitoring, at what frequency monitoring will be done, at what level of detail monitoring will be performed, and the distribution of monitoring reports.
- Independent audits may be conducted by the Sponsor in accordance with a quality oversight plan or equivalent to ensure monitoring practices are performed consistently and that monitors are following the CMP.

10 STATISTICAL CONSIDERATIONS

10.1 STATISTICAL DESIGN MODEL AND ANALYTICAL PLANS

Approximately 45 subjects (1:1 ratio of GRF6021 to placebo) will be enrolled in the study with the aim of having 40 evaluable subjects. Evaluable subjects are those who received all 4 doses and had all blood draws for assessment of the primary endpoint.

A Statistical Analysis Plan (SAP) with analytical details and assumptions will be developed and finalized before database lock and unblinding of the study data.

10.2 STATISTICAL HYPOTHESES

While we hypothesize that active treatment with GRF6021 will modulate the immune response to surgery, because this is an exploratory study, it is not designed to detect statistically significant differences between active and placebo on the primary endpoint. We will use a cell-signaling Elastic Net (csEN) approach to detect immune features (functional cellular attributes as well as cell abundance) that separate the active and placebo groups, and we hypothesize that active treatment will be associated with immunomodulatory changes that have previously been associated with improved clinical recovery. While a classical power calculation has not been performed, previous interventional studies from the Stanford group have demonstrated that a sample of 40 subjects is a pragmatic sample that enables the detection of clinically-relevant immunomodulatory changes, such as changes in signaling downstream of immune receptors, including interleukin-1 and Toll-like receptor 4.

For secondary endpoints, the statistical approach toward efficacy endpoints will be primarily descriptive; within-subject changes from baseline for each dosing group and among-group differences will be evaluated. The most important clinical outcomes will be the SRS (time to 50% recovery of the baseline score), WOMAC Pain (time to mild pain as indicated by a score <12/40), and WOMAC Physical Function (time to mild functional impairment as indicated by a score <18/60).

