4.2.2 SECONDARY ENDPOINTS

This study is not powered to detect statistically significant differences in outcomes. Secondary endpoints will be summarized over the study period from baseline values using descriptive statistics.

Secondary Endpoints:

- Change from baseline in 3D-CAM ([Inouye 2003](#))([Appendix 1](#)).
- Time to 50% recovery of the baseline value in the SRS ([Paddison 2011](#))([Appendix 2](#)).
- End of study treatment comparison of the Western Ontario and McMaster Universities Osteoarthritis Index (WOMAC) ([Bellamy 1986](#), [Bellamy 2002](#))([Appendix 3](#)).
- Time to a score of < 12/40 on a subset of questions from the WOMAC, Pain Subscale ([Bellamy 1986](#), [Bellamy 2002](#))([Appendix 3](#)).
- Time to a score of < 18/60 on a subset of questions from the WOMAC, Physical Function Subscale ([Bellamy 1986](#), [Bellamy 2002](#))([Appendix 3](#)).
- Change from baseline in the SF-36 ([Laucis 2015](#))([Appendix 4](#)).
- Change from baseline in the BDI-II ([Beck 1996](#))([Appendix 5](#)).
- Opioid analgesic consumption during hospital stay and after discharge to end of study.
- Time to discharge.
- Perioperative outcomes (e.g., surgery duration, anesthesia duration, PACU stay duration, ASA status, EBL, type and amount of intraoperative fluids administered, type and amount of intraoperative blood products, dose and type of anesthesia (general, regional), and intraoperative opioid dose).
- Change in functional status using the ActiGraph wearable device ([ActiGraph Corporation 2019](#)) providing measurements for physical activity/function and sleep (starting at least 3 days prior to surgery and continuing until the end of the study).
- Change from baseline in clinical laboratory parameters.
- Change from baseline in vital sign measurements.
- Change from baseline in ECG.
- The effects of GRF6021 on plasma proteomics.

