5 STUDY ENROLLMENT AND WITHDRAWAL

5.1 INCLUSION CRITERIA

In order to be eligible for inclusion, all subjects must meet the following criteria:

1. Men and women scheduled to undergo primary THA or TKA.
2. Aged 50-85 years at time of enrollment, inclusive.
3. Renal function as defined by estimated glomerular filtration rate (eGFR) ≥ 45 mL/min/1.73 m² using the Modification of Diet in Renal Disease (MDRD) study equation.
4. Female subjects must not be pregnant or breastfeeding. Women of childbearing potential (WOCBP) must have a negative pregnancy test at screening. WOCBP must agree to use acceptable forms of contraception ([Clinical Trial Facilitation Group](#)) prior to study entry. A woman is considered of

childbearing potential following menarche and until becoming postmenopausal (no menses for at least 2 years without an alternative cause). Should a woman become pregnant or suspect she is pregnant while she or her partner is participating in the study, she should inform her treating physician immediately.

5. The subject must understand and speak English and be able to understand and follow the study procedures, receive the treatment in the established timeframe, and continue during the follow-up interval.
6. Provide a signed and dated informed consent form in accordance with local regulations and/or IRB/IEC guidelines.

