15. Clinically significant abnormalities on screening electrocardiogram (ECG) that in the opinion of the investigator could put the subject at risk, including QTc intervals (using Fridericia's correction formula) of ≥ 450 ms in men and ≥ 470 ms in women.
16. Current, active liver disease: > 3-fold elevation of liver enzymes (alanine aminotransferase (ALT)

- and aspartate aminotransferase (AST) over upper limit of normal.
17. Clinically significant abnormalities in complete blood count (CBC), complete metabolic panel, serum albumin, or coagulation.
 18. History of a major infection (e.g. bacterial pneumonia) in the last 3 months, or recent minor infection (e.g. influenza, urinary tract infection) or fever (measured body temperature above 100.5 degrees F on 2 consecutive days) that in the assessment of the Principal Investigator could interfere with the primary endpoint.
 19. Severe anemia (hemoglobin < 8 g/dL).
 20. Urine protein-to-creatinine ratio (UPCR) of > 1.5 grams of protein per gram of creatinine.
 21. Inadequate venous access to allow IV drug delivery or multiple blood draws.
 22. Concurrent participation in any other therapeutic treatment trial. If there was prior clinical trial participation, subject must have discontinued investigational agents for at least 30 days for small molecules, and 1 year for active or passive immunotherapies prior to screening.
 23. Current diseases associated with significant alterations in immune function, including, but not limited to, autoimmune disease and cancer, except adequately-treated squamous or basal-cell carcinoma.
 24. Ongoing immunosuppressant treatment or within 5 half-lives of the treatment.
 25. History of substance abuse (alcohol, drugs of abuse) in the last 2 years.
 26. Functional impairment of major joint or lower extremity other than joint undergoing surgery.
 27. Any other condition and/or situation that the investigator believes may interfere with the safety of the subject, study conduct, or interpretation of study data.

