7.3.4 BASELINE: ON-SITE/TREATMENT

The on-site Baseline assessments will be gathered prior to the first infusion on Day 1. After the first infusion on Day 1, the subject will be discharged from the facility and come back the following morning (Day 2) for the inpatient period. The inpatient treatment period is 2 days during which each subject will receive 3 additional doses of 250 mL of their assigned treatment allocation (i.e., either GRF6021 or placebo).

Visits 3 through 5, Treatment (Days 1-3):

- Perform the following procedures on each day *prior* to administering (the first) study infusion:
 - Review AEs and concomitant medications.
 - 12-lead ECG (**Day 1 and 3 Only**).
 - Collect sample for CyTOF assessment (**Including second infusion on Day 2**).

- Obtain samples for proteomic assessments; fasting samples preferred (**Including second infusion on Day 2**).
- Collect vital signs (BP, HR, RR, and body temperature) (**Including second infusion on Day 2**).
- Targeted physical exam (**Day 1 and 3 Only**).
- Pregnancy testing for WOCBP (**Day 1 Only**).
- Administer 3D-CAM, SRS, and WOMAC (**Day 1 and 3 Only**).
- ActiGraph device data collection (**Day 1 and 3 Only**).
- Administer study treatment per the GRF6021 Infusion Administration Manual:
 - On the day before surgery (**Day 1**).
 - On the day of surgery within 4 hours before surgery start (first incision) (**Day 2**).
 - On the day of surgery upon arrival in the PACU (within 5 hours after the first incision) (**Day 2**).
 - On the day after surgery (**Day 3**).
- Perform the following assessments following each infusion start:
 - BP and HR at 15, 30, 45, and 60 min after infusion start.
 - Body temperature and RR at 60 minutes.
 - Collection of perioperative data (**Day 2 Only**, after second infusion).
 - Opioid consumption assessment (**Days 2 and 3 Only**).
 - 12-lead ECG (**Day 3+1 Only**, after end of last infusion).
 - Exit lab panel including pregnancy test (**Day 3 Only**, after end of last infusion).
 - Administer 3D-CAM (**Day 2 Only**, after second infusion).

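### Two leading clinical outcomes are times to a fixed WOMAC cut-off with no entry minimum, and nothing available adjusts them for the preoperative score

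*Protocol*

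**What the plan says.** Protocol section 10.2 ranks the clinical outcomes. It begins "The most important clinical outcomes will be the SRS (time to 50% recovery of the baseline score". For pain it then gives "WOMAC Pain (time to mild pain as indicated by a score <12/40"; the counterpart for function is "WOMAC Physical Function (time to mild functional impairment as indicated by a score <18/60". The SRS outcome is measured against the subject's own baseline. The two WOMAC outcomes are not.

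Section 4.2.2 defines the pain outcome as "Time to a score of < 12/40 on a subset of questions from the WOMAC, Pain Subscale"; its function entry reads "Time to a score of < 18/60 on a subset of questions from the WOMAC, Physical Function Subscale". Neither entry states when the clock starts or how a subject already below the cut-off is handled.

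On the joint to be replaced, section 5.1 asks only for "Men and women scheduled to undergo primary THA or TKA". The one functional exclusion in section 5.2, "Functional impairment of major joint or lower extremity other than joint undergoing surgery", concerns other joints and sets no minimum impairment of the operated one. Randomization strata are sex and joint (protocol 10.6.1, supplementary SAP 7.4).

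WOMAC is scored before surgery at Visit 2 and again on Day 1, where section 7.3.4 has "Administer 3D-CAM, SRS, and WOMAC" ahead of the infusion. It is then scored at Visits 5 to 15.

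Section 10.4.1 offers ANCOVA on the baseline value, or its rank version, for continuous endpoints, and a chi-square test or logit model for categorical ones. It names no method for time-to-event endpoints. Section 10.4.3 plans descriptive summaries and a between-group look for trends. The supplementary SAP (sections 5 and 6.2) assigns the WOMAC outcomes to a separate clinical SAP dated 08OCT2020, which is not among the documents reviewed.

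**The concern.** A subject's distance from an absolute cut-off before surgery is likely to be related to how soon that subject is below it afterwards. A subject who starts at 10/40 only has to return to the preoperative level, whereas one who starts at 30/40 has to improve by more than 18 points. With no entry minimum both can be enrolled, and with no WOMAC stratum nothing balances them between arms.

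The supplementary SAP reports 37 evaluable subjects, so about 18 per arm. Two or three extra low scorers in one arm could then look like faster recovery on GRF6021 or on placebo. The score needed to reveal and correct this is already collected, but the available text does not use it for these two outcomes.

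**Working it through.** **Plan's own figure.** There is none to reproduce: the documents give no WOMAC mean, SD, event count or effect size.

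**Step 1. The cut-offs.** 12/40 = 0.30 and 18/60 = 0.30. Items are scored on an 11-point scale (protocol 7.1.1.3.4). Taken as 0 to 10, the totals imply 4 pain items and 6 function items, and both cut-offs correspond to a mean item score below 3.

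**Step 2. Share below the cut-off before surgery.** Assumptions: whole-number scores, normal and truncated to the scale, mean 40% to 60% of the range, SD 15% to 20% of the range. For pain,

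p = [Φ((11.5 − m)/s) − Φ((−0.5 − m)/s)] / [Φ((40.5 − m)/s) − Φ((−0.5 − m)/s)].

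Example with m = 20, s = 8: (11.5 − 20)/8 = −1.0625, Φ = 0.1440; lower limit Φ(−2.5625) = 0.0052; upper limit Φ(2.5625) = 0.9948. So p = 0.1388/0.9896 = 0.140, and 37 × 0.140 = 5.2 subjects.

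| Assumed pain mean | SD 6 | SD 8 | Expected number of 37 |
|---|---|---|---|
| 24 | 1.9% | 5.9% | 0.7 to 2.2 |
| 20 | 7.8% | 14.0% | 2.9 to 5.2 |
| 16 | 22.4% | 27.3% | 8.3 to 10.1 |

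Function on the same relative scale gives 2.0% to 6.2%, 8.2% to 14.5% and 23.3% to 28.0%.

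**Step 3. Chance imbalance.** Assume the 37 split 18 and 19 (the split is not stated), with X₁ ~ Bin(18, p) and X₂ ~ Bin(19, p).

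| p | P(difference ≥ 2) | P(difference ≥ 3) |
|---|---|---|
| 0.02 | 0.07 | 0.01 |
| 0.05 | 0.23 | 0.06 |
| 0.10 | 0.40 | 0.16 |
| 0.14 | 0.47 | 0.23 |
| 0.23 | 0.56 | 0.33 |

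**Step 4. How far this can move a curve.** In an arm of 18, one subject is 1/18 = 5.6 percentage points of the cumulative event curve. Two are 11.1 points and three are 16.7. These are upper bounds at any one visit: they assume that every extra low scorer has crossed by then and would not have done so with a higher preoperative score.

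**Step 5. Does the available plan correct it?** The ANCOVA in 10.4.1 does not apply to a censored time. Between-group baseline testing in the same section might show an imbalance but would not adjust for it.

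**Step 6. Value of adjustment.** In simulations with 18 per arm and assumed recovery curves, adding the preoperative score to the time-to-score comparison raised power by about 0.02 to 0.06. The gain depends on how strongly preoperative and postoperative scores are assumed to be related; a weak relation gives less.

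**The case against.** The strongest reply is that the governing document is missing. Section 10.4.1 defers analytical details to the SAP, and the clinical SAP may already set the clock, the covariate and the rule for low baselines. This stands: the gap is shown only for the protocol and the supplementary SAP. The clinical SAP cannot supply an entry minimum, however.

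Second, time to a mild state is a legitimate absolute endpoint. A subject at 10/40 who worsens after surgery and returns below 12 has a meaningful time. This also stands, and is why the remedy is adjustment and not a new endpoint.

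Two stronger readings are tempting.

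- *A reader might infer that the plan counts subjects as recovered before surgery.* It does not say so. The time origin is unstated, but the study concerns postoperative recovery and the protocol's terms are mild pain and mild impairment. Silence on the origin is a detail to settle, not a rule that preoperative scores count.
- *A reader might infer that accepting one score below the cut-off, out of 11 postoperative assessments, generally pulls the treatment difference towards zero, so that confirmation at the next visit is needed.* Simulation does not bear this out. Assumptions: 18 per arm, two-sided log-rank test, and a control arm declining from 22–26 to a plateau of 8 with a 14-day time constant. If treatment shortens the time constant to 8 days, power is 0.17–0.27 for first crossing and 0.14–0.21 for confirmed crossing. If it lowers the plateau to 4, the figures are 0.15–0.25 and 0.24–0.32. With no effect both reject in 0.04–0.06 of trials. Confirmation is a trade-off.

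Last, chance imbalance affects every small trial, and section 4.2.2 says the study is not powered and these endpoints are descriptive. That limits the weight of the point but does not remove it.

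**Conclusion.** The point holds in a limited form. Two of the three leading clinical outcomes use an absolute cut-off, entry and stratification leave the preoperative WOMAC score uncontrolled, and no available text adjusts for it. Under the assumed distributions between about 1 and 10 of 37 subjects would start below the pain cut-off. An imbalance of two or more between arms is then anything from unlikely (about 0.07 at 2%) to more likely than not (0.56 at 23%). Every size here rests on assumed WOMAC means and SDs, and on an 18/19 split.

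This is an improvement worth making, not a flaw that endangers the study. The primary endpoint is CyTOF, and the documents attach no decision rule to the WOMAC times. If the clinical SAP already contains the adjustment, all that remains is to align the protocol wording.

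**What to change.** Check the clinical SAP of 08OCT2020 first. Where it is silent, state there and in protocol sections 10.2 and 10.4.3 that:

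1. Time runs from surgery, and only postoperative visits (Visit 5 onwards) can supply the event.
2. Each WOMAC time-to-score comparison is adjusted for the preoperative WOMAC score on the same question subset. The Visit 3 score, taken before the first infusion, is the natural choice, with Visit 2 if it is missing.
3. The number of subjects below each cut-off before surgery is reported by arm.
4. The comparison is repeated in subjects at or above the cut-off before surgery, as a sensitivity analysis.
5. A version confirmed at the next visit may be added as a further sensitivity analysis. First crossing stays the main definition.

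The cost is a few sentences and a few lines of code, with no new data or visits. The adjusted effect is conditional on the preoperative score and should be labelled so. Item 4 loses the subjects who start low, about 1 to 10 of 37 under the assumptions above. Enrollment has ended, so if these data are already unblinded, the additions should be reported as post hoc.
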